6.1 Population characteristics

Analyses for population characteristics will be performed for the safety population on the treatment groups if not stated otherwise. If the pharmacokinetic population, pharmacodynamic population, MTD population or efficacy population differ from the safety population, summary statistics and frequency tables for the respective population will be provided as well. The results will be displayed by region (Asia, ROW, and total), if reasonable.

6.1.1 Disposition

Disposition at the end of screening will be summarized for subjects who signed the informed consent for FGFR testing and for all subjects who signed the main informed consent, respectively. All enrolled subjects population comprises subjects who signed any informed consent. Disposition at the end of Treatment and for the Safety follow-up will be summarized by treatment groups for all subjects assigned to treatment.

6.1.2 Protocol deviations

Frequency tables of protocol deviations by category and deviation coded term will be summarized by treatment group.

6.1.3 Demographics and other baseline characteristics

Demographics and general baseline characteristics will be summarized by treatment group. Quantitative data will be summarized by arithmetic mean, SD, median, minimum and maximum. Frequency tables will be provided for qualitative data. Variables include sex, race, ethnicity, age (as reported on the eCRF), weight, height, body mass index (BMI), and NYHA functional class.

Baseline cancer characteristics will be summarized by treatment group. Variables include for example baseline ECOG Performance Status, number of target lesions, number of non-target lesions, cancer type, histology, status of primary tumor, stage at initial diagnosis, grading at initial diagnosis, clinical status at study entry, stage at study entry, time since initial diagnosis. Please note that the list of the above mentioned parameters is not extensive.

In addition, demographics and baseline cancer characteristics will be summarized for all subjects who signed the informed consent for FGFR testing.

6.1.4 Prior and Concurrent Medication/Therapy

Prior anti-cancer therapy and surgical therapeutic procedures will be summarized by treatment group. The counts and percentages of patients who were previously treated using radiotherapy, local anti-cancer therapy, systemic anti-cancer therapy, and who had any diagnostic and therapeutic procedure(s) will be presented. The number of patients with radiotherapy and systemic or local anti-cancer therapy will be presented by intent of procedure and number of regimens/procedures. In addition, concurrent radiotherapy, diagnostic and therapeutic procedures will be summarized. Prior and concomitant medications will be coded to generic terms using the World Health Organization Drug Dictionary (WHO

Statistical Analysis Plan

Protocol No.: **BAY 1163877/16443**

Page: 14 of 20:

DD) Version 2017SEP or later and summarized by treatment group. The version used in analyses will be presented in the clinical study report.

6.1.5 Medical History

Medical history data will be coded using the Medical Dictionary for Regulatory Activities (MedDRA) Version 20.1 or later. The version used in analyses will be presented in the clinical study report. Medical history data will be summarized by system organ class, high level term, and preferred term by treatment group.

6.2 Efficacy

Efficacy analyses will be performed on the efficacy analysis set.

Tumor response

Efficacy data, such as best tumor response, will be summarized using descriptive statistics and will be graphically displayed if appropriate. The correlation between PD parameters and selected safety, efficacy, or PK parameters may be graphically displayed. Further statistical analyses may be conducted.

The efficacy analysis will include descriptive analyses on response rate, progression-free survival (PFS), time to progression (TTP), duration of response (DOR), and duration of treatment (DOT).

Response as defined by RECIST v.1.1: complete response (CR), partial response (PR), stable disease (SD), progressive disease (PD). Response and progression will be evaluated in this trial using the new international criteria proposed by the RECIST committee for solid tumor.

PFS is defined as the time (days) from the date of the first dose of study drug to the date of the first observed disease progression (radiological or clinical) or death due to any cause, if death occurs before progression is documented. PFS for subjects without tumor progression at the time of analysis will be censored at their last date of tumor evaluation.

TTP is defined as the time from start of study treatment until first observed disease progression (radiological or clinical). In comparison to PFS, TTP does not consider death as an event.

DOR (for partial and complete response (PR/CR)) is defined as the time (days) from the first documented objective response of PR or CR, whichever is noted earlier, to disease progression or death (if death occurs before progression is documented).

Kaplan-Meier (KM) product-limit estimates for median, 25th and 75th percentile with its 95% CI together with total number of subjects, total censored and total events will be provided for PFS and TTP per treatment. In addition KM survival curves will be presented for each treatment group.

Best overall tumor response according to RECIST criteria will be summarized by treatment group and region (Asia, ROW, and total) using frequency counts.

Best % Change in Target Lesion sum of diameter from Baseline will be displayed graphically for all subjects from worst to best in a waterfall plot.

Subgroup analysis will be performed by prior immunotherapy information (prior immunotherapy vs. no prior immunotherapy) .

Statistical Analysis Plan

Protocol No.: BAY 1163877/16443

Page: 15 of 20:

6.3 Pharmacokinetics/pharmacodynamics

6.3.1 Pharmacokinetics

Analyses will be performed on the Pharmacokinetic analysis set. A pooled treatment group (all 800mg BID patients, regardless of study part or tumor type) will be included for PK analyses.

The concentration-times courses of all analytes will be tabulated for each cohort by treatment group. The following statistics will be calculated for each of the sampling points: arithmetic mean, standard deviation, and coefficient of variation (CV), geometric mean, geometric standard deviation (re-transformed standard deviation of the logarithms), minimum, median, maximum value, and the number of measurements. Means at any time will only be calculated if at least 2/3 of the individual data were measured and were above the lower limit of quantification (LLOQ). For the calculation of the mean value, a data point below LLOQ will be substituted by one half of this limit. In tables showing mean values, where values below LLOQ are included in the calculation of mean values, these means will be marked.

Individual and geometric mean concentration vs. time curves of all analytes (using the actual sampling times for individual plots and the planned sampling times for mean plots) will be plotted by cohort using both linear and semilogarithmic scale.

The amount and percent of drug excreted into urine will be graphically illustrated for the sampling interval as well as for the whole sampling period (bar-charts for the individual data and the arithmetic mean including standard deviation).

Pharmacokinetic characteristics (t_{max} , t_{last} , and $\%AUC(t_{last} - \infty)$ excluded) will be summarized by the statistics mentioned above. t_{max} and t_{last} will be described utilizing minimum, maximum, and median as well as frequency counts.

PK Dose proportionality

To investigate dose proportionality, an explorative ANOVA, including the factor cohort, will be performed on the log-transformed values of C_{max}/D , $AUC(0-t_{last})/D$, and AUC/D calculated from single (where applicable) and multiple dose PK profiles.

Bridging: tablet vs solution relative bioavailability

PK parameters of different dose levels will be analyzed together for the assessment of relative bioavailability.

In order to evaluate the relative bioavailability of the tablet formulation, tablet C_{max}/D , $AUC(0-t_{last})/D$, and AUC/D on Cycle 1, Day -3 will be compared to solution C_{max}/D , $AUC(0-t_{last})/D$, AUC/D on Cycle 1, Day 1 for all analytes. If needed, additional PK parameters may be used for relative bioavailability assessment. The logarithms of these PK parameters will be analyzed using analysis of variance (ANOVA) including subject and formulation effects.

Based on these analyses, point estimates (LS-means) and exploratory 90% confidence intervals for the ratios (tablet/solution) of C_{max}/D , $AUC(0-t_{last})/D$, and AUC/D will be calculated by re-transformation of the logarithmic data using the intra-individual standard deviation of the ANOVA.

Subjects to be included in the relative bioavailability evaluation ("tablet bridging cohort") should have evaluable pharmacokinetic data on both Cycle 1, Day -3 and Cycle 1, Day 1.

Food effect

Statistical Analysis Plan

Protocol No.: **BAY 1163877/16443**

Page: 16 of 20:

In order to evaluate the effect of food on BAY 1163877, C_{max} and $AUC(0-t_{last})$ on Cycle 1, Day -3 and C_{max} and $AUC(0-t_{last})$ on Cycle 1, Day 1 will be compared. The logarithms of C_{max} and $AUC(0-t_{last})$ will be analyzed using ANOVA including subject and food effect.

Based on these analyses, point estimates (LS-means) and exploratory 90% confidence intervals for the ratios (high-fat, high-calorie meal / fasting) of C_{max} and $AUC(0-t_{last})$ will be calculated by re-transformation of the logarithmic data using the intra-individual standard deviation of the ANOVA.

The PK parameters C_{max}/D , $AUC(0-t_{last})/D$, AUC/D , C_{max} and $AUC(0-t_{last})$ will be graphically illustrated using stickplots. Scatterplots of the PK parameters C_{max}/D , $AUC(0-t_{last})/D$, AUC/D will be created.

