PR	Partial response
Qd	Probability of dose being the MTD
RECIST	Response Evaluation Criteria in Solid Tumors
RMAD	Relative Median Absolute Difference
ROW	Rest of the world
RP2D	Recommended Phase II dose
SAE	Serious adverse event
SAP	Statistical Analysis Plan
SAS	Statistical Analysis System
SCCHN	Squamous cell carcinoma of the head and neck
SD	Stable disease
SD	Standard deviation
sqNSCLC	Squamous non-small cell lung cancer
Td	(Tolerable) Probability that the DLT rate is <0.20 , $Pr(p <0.20 d)$, for a dose d
TEADR	Drug-related adverse event
TEAE	Treatment-emergent adverse event
t_{last}	Time to last observed concentration
t_{max}	Time to maximum observed concentration
TTP	Time to progression
vs	Versus, as opposed to
WHO DD	World Health Organization Drug Dictionary

1. Introduction

Fibroblast growth factors (FGF) and their corresponding receptor family (FGFR) drive crucial oncogenic signaling pathways including cell proliferation, survival and migration. FGFRs are commonly altered in various human tumor diseases, including FGFR1 amplification in squamous non-small cell lung cancer (sqNSCLC) or activating mutations of FGFR3 in bladder cancers. These changes contribute to tumor cell growth, sustained angiogenesis, invasion and metastasis and resistance against other therapies.

Rogaratinib (BAY 1163877) is an oral inhibitor of FGFR1, 2 and 3 and showed strong anti-tumor efficacy in pre-clinical models as a single agent as well as in combination with cytotoxic agents in FGFR pathway addicted tumor models.

The targeted application form is oral and preclinical data suggest low clearance and low volume of distribution resulting in a daily dose of 300 to 800 mg.

Further details can be found in the investigator's brochure (IB) (1), which contains comprehensive information on the study drug. The IB is available in the Trial Master File.

Additional information elaborating on the rationale of the study and the benefit-risk assessment can be found in the protocol.

This Statistical Analysis Plan (SAP) is based on the Clinical Study Protocol version 7.0 (including Amendment 7.0) (2).

2. Study Objectives

The primary objectives of this study are:

- To determine the safety and maximum tolerated dose (MTD) of BAY 1163877 in subjects with advanced solid organ malignancies

Statistical Analysis Plan

Protocol No.: **BAY 1163877/16443**

Page: 5 of 20:

- To characterize the pharmacokinetics (PK) of BAY 1163877

The secondary objectives of this study are:

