Subjects will continue receiving treatment until tumor progression, unacceptable toxicity, consent withdrawal, or subject withdrawal from the study at the discretion of the Investigator or his/her designated associate(s). As long as, in the judgment of the subject and the investigator, some benefit with evidence of tumor reduction or stable disease is being derived, dosing with BAY 1163877 may continue.

Determination of the MTD

An adaptive dose escalation design will be used to determine the MTD in study Part 1 / dose escalation (all comer). The MTD is defined as the highest dose that can be given such that not more than 20% of subjects experience a DLT during Cycle 1.

Without the occurrence of toxicities, dose escalation could be stopped and RP2D may be determined based on PK and/or PD results. The decision to continue treatment for an individual subjects will be made by the investigator according to the criteria specified in the protocol.

Each cohort will be evaluated after all subjects have completed the first 21 days of treatment (which will subsequently referred to as “Cycle 1”) or early discontinued.

Statistical Analysis Plan

Protocol No.: **BAY 1163877/16443**

Page: 9 of 20:

Safety monitoring will occur by telephone conferences with participation of the investigators and the sponsor on a regular basis.

At the time of dose escalation the available clinical safety information is discussed in a telephone conference by the involved investigators and representatives from the Sponsor including the Study Medical Expert as well as representatives of other clinical and if required further contributing functions (drug safety monitoring team – DSMT). During this telephone conference it will be judged if dose escalation can proceed as planned according to the procedure outlined below. Dose escalation for subsequent cohorts will only be considered after full evaluation of at least Cycle 1 safety data from the previous cohort.

The National Cancer Institute (NCI) Common Terminology Criteria for Adverse Events Version 4.03 (CTCAE v4.03) will be used to grade toxicities / adverse events.

The dose escalation will be performed as follows:

- Initially 3 subjects per dose level will be enrolled. In case 2 or more sites are conducting the dose escalation part, the initial enrolment of 4 subjects per dose level is optional.

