- The starting dose of BAY 1163877 is 50 mg given as a single dose on Cycle 1, Day 1, and twice daily (b.i.d.) from Cycle 1, Day 3 (100 mg / day).
- The maximum dose escalation will be 2-fold.
- Possible daily doses of BAY 1163877 starting from 100 mg in increments of 100 mg.
- The possible maximum dose of BAY 1163877 is considered to be 550 mg b.i.d. (1100 mg / day). Higher doses might be explored after discussions between sponsor and investigators.
- If at least 1 subject out of 3 or 1 out of 4 in a cohort has DLTs or if at least 2 subjects report drug-related AEs (CTCAE v4.03) of Grade ≥ 2 , any further dose escalation, de-escalation or cohort expansion will be decided in consultation between all investigator(s), and the sponsor (within the DSMT) after consideration of all available safety data of the previous cohorts. Any subsequent dose will be selected in order to determine the MTD.

Model-based dose-response analysis of the DLT rates will be performed during these interim reviews in order to guide the dose decision. The model-based dose selection procedure is considering data at all dose levels (not just at the last cohort). The dose predicted to yield 20% DLT rates will be reported from that model as a best candidate for the next cohort.

The final decision about the next dose will be made by the sponsor in consultation with all investigators (DSMT).

If the selected dose is larger than the last dose tested, then escalation will be pursued. If it is lower, a de-escalation step will occur.

Cohort expansion will occur when a previously tested dose is selected again for the next cohort of 3 subjects.

Expansions at any given dose up to a total of 9 subjects are allowed. In principle, the selection of a next dose level where the predicted DLT rate is close to 20% should insure that the next dose tested will remain safe.

Statistical Analysis Plan

Protocol No.: **BAY 1163877/16443**

Page: 10 of 20:

Nevertheless, the following constraint will be added in order to protect subject safety during the adaptive dose selection decisions:

- If 2 out of 3 (or 2 out of 4), at least 4 out of 6 (or at least 5 out of 9) subjects experience DLTs at a given dose level, only lower doses will be given in all subsequent cohorts because the probability that the dose is above the MTD is very large (above 95.4%).
- The dose-escalation procedure will be stopped as soon as:

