4.1 General Principles

The statistical evaluation will be performed by using the software package SAS release 9.2 or higher (SAS Institute Inc., Cary, NC, USA), R release 2.4.1 or higher and BRugs release 0.3-3 or higher. All variables will be analyzed by descriptive statistical methods. The number of data available, mean, standard deviation, minimum, median, and maximum will be calculated for metric data. Frequency tables will be generated for categorical data.

Data displays will follow the standard table catalogs for oncology standards, global standards, and clinical pharmacology standards, respectively.

The pharmacokinetic parameters will be evaluated statistically in accordance with pertinent company guidelines.

The following treatment groups will be analyzed:

- Total Dose Escalation – It contains all cohorts from the escalation phase:
 - 100 mg BAY 1163877 (50 mg solution BID)
 - 200 mg BAY 1163877 (100 mg solution BID)
 - 400 mg BAY 1163877 (200 mg tablet BID)
 - 800 mg BAY 1163877 (400 mg tablet BID)
 - 1200 mg BAY 1163877 (600 mg tablet BID)
 - 1600 mg BAY 1163877 (800 mg tablet BID)
- Expansion All Comers – Expansion phase, 1600 mg BAY 1163877 (800 mg tablet BID), cancer type does not fit the categories below
- Expansion Bladder – Expansion phase, 1600 mg BAY 1163877 (800 mg tablet BID), cancer type: bladder cancer

Statistical Analysis Plan

Protocol No.: **BAY 1163877/16443**

Page: 11 of 20:

- Expansion Head & Neck – Expansion phase, 1600 mg BAY 1163877 (800 mg tablet BID), cancer type: squamous carcinoma cell head and neck
- Expansion NSCLC – Expansion Phase, 1600 mg BAY 1163877 (800 mg tablet BID), cancer type: lung adenocarcinoma / squamous cell carcinoma

The categories of region used for subgroup analysis will be derived for each subject by using the variable country (location of the respective site).

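### SAP 6.3.1 gives dose proportionality an exploratory cohort ANOVA with no slope, ratio or interval; add a power-model slope with a 90% CI that allows for formulation

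*SAP*

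**What the plan says.** Section 2 lists "To characterize the pharmacokinetics (PK) of BAY 1163877" as a primary objective. The analysis of dose proportionality is one sentence in section 6.3.1: "To investigate dose proportionality, an explorative ANOVA, including the factor cohort, will be performed on the log-transformed values of" C_max/D, AUC(0-t_last)/D and AUC/D, from single-dose (where applicable) and multiple-dose profiles. The sentence is the same in SAP version 1.0 and in the later version. Neither states an estimate, interval, significance level or criterion.

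The same section treats its other two ANOVAs differently. For the tablet bridging it promises "point estimates (LS-means) and exploratory 90% confidence intervals for the ratios (tablet/solution", and the food-effect paragraph does the same for fed against fasting. Scatterplots of the dose-normalised parameters and geometric means are also planned.

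On numbers, section 3 says "Initially 3 subjects per dose level will be enrolled", that "the initial enrolment of 4 subjects per dose level is optional" when two or more sites take part, and that "Expansions at any given dose up to a total of 9 subjects are allowed". Section 4.1 of the later version lists six dose groups. 50 and 100 mg b.i.d. are given as solution; 200, 400, 600 and 800 mg b.i.d. as tablet. Section 6.3.1 of that version adds a pooled group of all 800 mg b.i.d. subjects for PK analyses.

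**The concern.** A one-factor ANOVA on dose-normalised values asks whether all cohort means are equal. It ignores the order of the doses and spreads a steady trend over 5 numerator degrees of freedom. On its own it yields no measure of how far exposure departs from proportionality. If its overall test is what gets reported, it can count against proportionality. It can appear to support proportionality only by failing to reject, which with small cohorts says little.

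At stake is what the report can say about exposure per unit dose over a 16-fold range (50 to 800 mg b.i.d.), which is part of a primary objective. A reader could take a non-significant ANOVA as reassurance when the data cannot exclude a halving of dose-normalised exposure.

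**Working it through.** The SAP states no power, alpha or CV for this analysis, so there is no figure to reproduce.

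**Inputs from the SAP.** Doses 50, 100, 200, 400, 600, 800 mg (4.1); 3 or 4 per dose, up to 9 (section 3); 20 evaluable all-comers at the MTD, at least 12 Part 2 subjects sampled for PK, about 40 in Part 3 (section 3).

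**Assumptions.** Between-subject CV 30-60%; overall test at 5%; true power-model slope b = 0.75, so dose-normalised exposure at 800 mg is 16^(−0.25) = 0.50 of that at 50 mg.

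**Overall ANOVA test.** With x = ln(dose), σ² = ln(1 + CV²) and Sxx = Σ n(x − x̄)², the non-centrality is λ = (b − 1)²·Sxx/σ².
- 3 per dose: Sxx = 17.43, so λ = 0.0625 × 17.43/0.1484 = 7.34 at CV 40%, 4.88 at 50%, 3.54 at 60%. The critical value of F(5, 12) is 3.106.
- 4 per dose: Sxx = 23.24, so λ = 9.79, 6.51, 4.72. The critical value of F(5, 18) is 2.773.

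Probability that the overall test misses slope 0.75:

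| Layout | CV 30% | CV 40% | CV 50% | CV 60% |
|---|---|---|---|---|
| 3 per dose | 42% | 65% | 76% | 82% |
| 4 per dose | 21% | 48% | 65% | 74% |
| 3 per lower dose, 23 pooled at 800 mg (3 + 20) | 6% | 27% | 47% | 61% |
| 3 per lower dose, 75 pooled at 800 mg (3 + 20 + 12 + 40) | 1% | 13% | 32% | 48% |

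**Power-model slope, all doses, no formulation term.** SE(b) = σ/√Sxx. With 3 per dose the 90% CI half-width is 1.746 × 0.385/√17.43 = 0.16 at CV 40% and 0.23 at CV 60%. A 5% slope test misses b = 0.75 in 28%, 45% and 58% of trials (CV 40, 50, 60%).

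**Formulation is tied to dose.** Suppose PK is truly proportional but the tablet/solution ratio is 0.8 (assumed). The unadjusted slope shifts by ln(0.8) × Σ_tablet n(x − x̄)/Sxx = −0.223 × 7.34/17.43 = −0.09 with 3 per dose. At a ratio of 0.7 the shift is −0.357 × 0.421 = −0.15. The cohort ANOVA has the same confounding: it cannot tell a formulation step from a dose effect.

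**Slope with a formulation term, 3 per dose.** Only variation in dose within each formulation counts: 0.72 (50-100 mg) + 3.25 (200-800 mg) = 3.97, or 3.97/17.43 = 23% of the information.
- Half-width = 1.753 × 0.385/√3.97 = 0.34 at CV 40%, 0.49 at CV 60%.
- The slope test misses b = 0.75 in 77%, 83% and 87%, no better than the ANOVA.
- Over 16-fold, the highest-to-lowest ratio is known to within a factor of 16^0.34 = 2.6 to 16^0.49 = 3.9 either way.

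**Tablet doses only, 3 per dose.** Half-width = 1.812 × 0.385/√3.25 = 0.39 at CV 40%, 0.56 at CV 60%. Over the 4-fold tablet range that is a factor of 4^0.39 = 1.7 to 4^0.56 = 2.2.

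**The case against.** A reader might infer that the SAP will take a non-significant F-test as proof of proportionality. It does not say so. It names no F-test, p-value or decision rule and calls the ANOVA explorative. A cohort ANOVA can also yield least-squares means and ratios between doses with intervals, which is how the section uses ANOVA for formulation and food. So the fault is an unspecified output, not a stated misreading.

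A reader might also infer that clear non-proportionality would usually be missed. That does not hold in general. It fails with 3 per dose at CV 30% (42% missed), and with 75 pooled at 800 mg it fails throughout CV 30-60%. The SAP gives neither the CV nor the size of departure, and does not say whether cohort means dose level, treatment group or the pooled group.

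Third, a power model without a formulation term would put a fairly narrow interval around a possibly biased slope. This stands, and it changes the remedy: once formulation is separated, the power advantage disappears. Nor is the slope test uniformly better. For a plateau above 400 mg (3 per dose, CV 30%) its power is 66%, against 68% for the overall test.

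Finally, geometric means and scatterplots could show a gross departure. True, but they put no interval on it. The word explorative does not explain the gap, since the neighbouring intervals are exploratory too and are still specified.

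**Conclusion.** The point holds as a gap in what the analysis will deliver. The only inferential method for dose proportionality has no specified slope, ratio or interval, unlike its two neighbours in the same section, although it serves a primary objective. If it is read through its overall test, a halving of dose-normalised exposure over the range is missed in 65-82% of trials with 3 per dose and 48-74% with 4. Those figures rest on an assumed CV of 40-60%, slope 0.75 and a 5% level; they fall at CV 30% or with a pooled 800 mg b.i.d. group. The documents do not support saying that non-significance will be reported as proportionality, only that it could be mistaken for it. The case for a power model rests on an estimate whose uncertainty is visible, not on higher power.

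**What to change.** In section 6.3.1 keep the ANOVA and add an exploratory power model, log(parameter) = a + b·log(dose).
- Report b, and the implied ratio of dose-normalised exposure over the dose range, each with a 90% CI.
- Fit it with a formulation term or within the tablet doses (200-800 mg b.i.d.), with the all-dose fit without that term as a sensitivity analysis.
- Use all 800 mg b.i.d. subjects as one dose level.
- State that a non-significant ANOVA is not evidence of proportionality.

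The cost is a few lines of SAP text and a few simple regressions per parameter on data already collected. The model assumes a log-linear trend, which the retained ANOVA and the planned scatterplots can check. The interval is wide once formulation is separated (about ±0.34 to ±0.49 for b with 3 per dose at CV 40-60%), and the report should show that width.
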